7.3.4 Transition Visit (Week 2, 4, or 8)

Subjects may transition at Weeks 2, 4, or 8 if they have achieved a minimum Remodulin dose of 20 ng/kg/min and the Investigator deems the subject suitable for transition. Subjects will transition from Remodulin to Orenitram over the course of 1 to 21 days in an inpatient or outpatient setting using a cross-taper method (ie, decreases in Remodulin dose coincide with increases in Orenitram dose). Subjects will be instructed to take the appropriate number of Orenitram tablets based upon their Remodulin dose and the transition schedule chosen by their healthcare provider.

At the discretion of the Investigator, transition may also be reversed or stopped if necessary due to significant signs or symptoms of PAH or due to serious safety concerns. If the Investigator deems a subject unsuitable for transition to Orenitram due to significant signs and symptoms of PAH or any other serious safety concerns, the subject may remain on Remodulin for the duration of the study. However, the subject should be continually assessed to determine if they become stable enough for transition to Orenitram. All subjects still on Remodulin at Week 8 should transition to Orenitram at Week 8 regardless of their Remodulin dose unless the Investigator deems them unsuitable for transition to Orenitram due to significant signs and symptoms of PAH or any other serious safety concerns.

Transition will occur as follows:

- The dose of Remodulin can be reduced no more than 10 ng/kg/min per day for transitions in the outpatient setting. For inpatient transitions, there is no limit on the rate of Remodulin dose reduction.
- The target dose of Orenitram at the end of transition is dependent on the subject's weight and Remodulin dose. Up-titration of Orenitram should coincide with a reduction in the Remodulin dose. The target TDD of Orenitram at the end of

transition will be calculated based upon the following equivalence weight-based formula:

TDD [mg] = 0.0072 * Remodulin dose [ng/kg/min] * weight [kg].

- The Orenitram up-titration dose should be taken at approximately the same time the Remodulin dose is decreased.
- Examples of transition schedules for various subject body weights and Remodulin doses are listed in Appendix I.

The following subject-reported data will be completed by the subject at the Transition Visit prior to all other assessments and prior to initiation of Orenitram: emPHasis-10 questionnaire and TSQM.

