2.2.1 Overview

The study is a 16-week, open-label, multicenter, uncontrolled study in subjects with PAH.

The following study visits will occur during the 16-week study at the following time points:

- Screening
- Baseline
- Week 2 (Day 15 [±3 days]), Week 4 (Day 29 [±5 days]), Week 8 (Day 57 [±5 days]),
 Week 12 (Day 85 [±5 days]), and Week 16/Early Study Withdrawal (Day 113[±7 days])
- Transition Visit may occur at Weeks 2, 4, or 8 if the subject has achieved a minimum Remodulin dose of 20 ng/kg/min and the Investigator deems the subject suitable for transition. Transition may be reversed or stopped if necessary due to significant signs or symptoms of PAH or due to serious safety concerns.
- Post Transition Visit (7 to 14 days after the Transition Visit)

Table 1 Overall Schedule of Time and Events

	Screening	Baseline ^{a,b}	Treatment Phase						
Study Visit/Week			Week 2s	Week 4s,v	Week 8s	Post Transition Visit ^v	Week 12	Week 16/ Early Study Withdrawal ^c	
Day	-28 to -1	-14 to -1	15 (±3 days)	29 (±5 days)	57 (±5 days)	7 to 14 days after Transition Visit ^v	85 (±5 days)	113 (±7 days)	
Informed consent	X								
Inclusion and exclusion criteria assessment	X	X							
Demographics	X								
PAH history ^d	X								
TSQM ^e		X		X ^s				X	
emPHasis-10 questionnaire		X		X ^s				X	
PAH symptom score		X		X ^s				X	
WHO FC	X	X	X	X	X	X	X	X	
Swan-Ganz right heart catheterization ^f	X								
Medical history	X	X						[
Prior PAH medicationsg	X	X							
Concomitant medicationsgh	X	X	X	X	X	X	X	X	
Physical examinationi	X			X ⁵				X	
Vital signs ^j	X	X	X	X	X	X	X	X	
CD4 count (for subjects with human immunodeficiency virus)	X								

	Screening ^a	Baseline ^{a,b}	Treatment Phase						
Study Visit/Week			Week 2s	Week 4s,v	Week 8s	Post Transition Visit ^v	Week 12 85 (±5 days)	Week 16/ Early Study Withdrawal ^c 113 (±7 days)	
Day			15 (±3 days)	29 (±5 days)	57 (±5 days)	7 to 14 days after Transition Visit ^v			
Clinical laboratory parameters (serum chemistry and hematology)	х	х	Xs					x	
Urine pregnancy test ^k	X	X	X ^s	X	X		X	X	
Echocardiogram		X		X ^s				X	
Serum NT-proBNP ¹	X	X		X*				X	
Blood sample for pharmacogenomics (genetic/RNA) ^m		X							
Blood sample for biomarker evaluation (optional) ^m		х		Xs				х	
6MWT followed by heart-rate recovery (1 minute) and Borg dyspnea score ⁿ	х	х	X°.p	Xop	X ^{o,p}	X^p	X^p	X^p	
Study drug dosing ^q		$X^{r,t}$	$X^{r,t}$	$X^{r,t}$	$X^{r,t}$	$X^{r,t}$	$X^{r,t}$	X ^{r,t}	
Recording of adverse events	X	X	X	X	X	X	X	X	

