- At the Transition Visit, 6MWT should occur with the subject still on Remodulin therapy, before initiating the transition to Orenitram.
- P When the subject is receiving Orenitram, the 6MWT should occur within 2 to 6 hours of the subject's most recent dose.
- 9 Study drug refers to both Remodulin and Orenitram.
- If the Investigator deems a subject unsuitable for transition to Orenitram due to significant signs and symptoms of PAH or any other serious safety concerns, the subject may remain on Remodulin for the duration of the study. The Investigator may reverse, or stop the transition to Orenitram due to concerns of subject safety.
- In addition to the scheduled assessments, additional testing will be performed at the Transition Visit as indicated. Subjects may transition at Weeks 2, 4, or 8 if they have achieved a minimum Remodulin dose of 20 ng/kg/min and the Investigator deems the subject suitable for transition. Transition may be reversed or stopped for subject safety.
- Subjects should be optimized on Remodulin therapy prior to transition to Orenitram; a dose should be achieved that improves the symptoms of PAH while minimizing excessive pharmacologic effects of Remodulin. Transition from Remodulin to Orenitram will occur over the course of 1 to 21 days.

- ^u The study site will contact subjects daily during the first 2 weeks of the study, daily during the transition period (ie, while the subject is on both Remodulin and Orenitram), and twice weekly for the first 2 weeks after transitioning (ie, while the subject is on Orenitram and no longer on Remodulin). At all other time points during the study, subjects will be contacted once weekly.
- The Post Transition Visit occurs 7 to 14 days after transition from Remodulin to Orenitram is initiated. If the Transition Visit occurs at Week 2, the Week 4 visit can be substituted for the Post Transition Visit (ie. an extra visit is not necessary).
- W Study site or pharmacy personnel should assess drug returned and dosing information to confirm drug accountability.

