3.1.4 Definition of Treatment Phases

"Remodulin phase" is defined as the portion of the study when a patient is receiving Remodulin only.

"Transition phase" is defined as the portion of the study beginning at the Transition Visit when a patient is receiving both Remodulin and Orenitram. "Transition phase" ends at the last dose of Remodulin if the transition is "successful". "Transition phase" ends at the last dose of Orenitram if the transition is "unsuccessful" and reversed. "Transition phase" ends at the last dose of Orenitram and Remodulin if the transition is stopped.

"Orenitram phase" is defined as the portion of the study when a patient is receiving Orenitram only.

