3.7.1 Adverse Events (AEs) and Prostanoid AEs

Adverse events will be captured from when the subject signs the informed consent form (ICF) until the subject completes the study or is withdrawn from the study. All AEs will be coded to system organ class and preferred term using MedDRA version v 21.0. Treatment-emergent adverse events (TEAEs) are defined as AEs that start after the first dose of Remodulin.

Adverse events related to study drug will be those with a causality of possibly or probably related.

The severity of a given AE is the maximum of all severities recorded during initial recording and all reassessments of the AE.

An overview of AEs will be provided including counts and percentages of subjects and event counts (an AE record regardless of reassessment, only contributes once into the event count) with the following:

- Any TEAEs (overall and by maximum severity)
- Any serious AEs (SAEs)
- Any treatment-emergent serious AEs (TESAEs)
- Any TEAEs leading to discontinuation of study
- Any TEAEs leading to discontinuation of Remodulin
- Any TEAEs leading to discontinuation of Orenitram
- Any SAEs leading to death

Counts and percentages of subjects and event counts will also be presented by system organ class and preferred term for each of the categories in the overview, except SAEs, if there are at least 5 adverse events in the categories.

Figures for visualizing the number of days an AE falls into each AE severity category (Mild, Moderate, Severe) and changes in AE severity over time may be provided by sponsor.

For each of the "Prostanoid AEs" defined by section 3.3.1.9 of the protocol (headache, diarrhea, nausea, flushing, jaw pain, extremity pain, and vomiting):

- The counts and percentages of patients and event counts who report the Prostanoid AE will be summarized, as well as a breakdown of the maximum severity reported (e.g. mild, moderate, severe).
- This will be reported separately for each treatment phase.
- AEs that occur in more than one treatment phase (e.g. a 'severe' headache that began
 in the Remodulin phase that continued as a 'severe' or 'mild' to the Transition phase will
 be counted in both treatment phases, with corresponding severities based on the
 maximum severity in each phase) will be counted in each treatment phase.
- Changes in severity of Prostanoid AEs over the entire study period may be listed, summarized, and/or depicted graphically for each patient. This may be performed by the study sponsor.

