- The number of days which the AE was reported and the corresponding severity may be summarized for each treatment phase (i.e. Remodulin phase, Transition phase, Orenitram phase). For these summaries, the AE Reassessment date will be used as the start and end dates for an AE which changes in severity, and the AE End Date will be the end date for the AE. This may be performed by the study sponsor.

Example:

Headache occurring in Remodulin phase

AE Start Date: 1/10/2022 severity: mild

AE Reassessment Date 1: 1/22/2022 severity: moderate
AE Reassessment Date 2: 2/01/2022 severity: moderate

AE End Date: 2/05/2022

Mild: 12 days (1/10/2022 to 1/22/2022)

Moderate: 14 days (1/22/2022 to 2/5/2022)

Severe: 0 days

A by subject listing will be provided for all of the AEs and listings will also be presented specifically for SAEs and TEAEs leading to discontinuation of study drug.

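### Prostanoid AEs are tabulated by treatment phase as crude counts and percentages, without regard to time in phase or to who entered it

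*SAP*

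**What the plan says.** For each of seven prostanoid effects, SAP 3.7.1 states: "The counts and percentages of patients and event counts who report the Prostanoid AE will be summarized", with a breakdown by maximum severity. It continues: "This will be reported separately for each treatment phase". For "AEs that occur in more than one treatment phase", the rule is to count the event in every phase it touches, with that phase's own maximum severity. SAP 3.7 bases safety summaries on the Safety Population, meaning everyone who received either drug (SAP 3.2.1). No narrower denominator is given for a phase, and neither document plans a rate per unit of subject-time.

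SAP 3.1.4 defines the phases as Remodulin only, both drugs, and Orenitram only; the last "is defined as the portion of the study when a patient is receiving Orenitram only". SAP 2.2.1 fixes the timing: "Transition Visit may occur at Weeks 2, 4, or 8", and "Transition from Remodulin to Orenitram will occur over the course of 1 to 21 days". Protocol 6.1 and 7.3.4 allow a subject judged unsuitable for transition to stay on Remodulin for the whole study.

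SAP 3.7.1 also describes a summary of AE days by severity and phase. It is optional and is not divided by days in phase. SAP 3.3.7 summarises days on each drug, time to transition and duration of transition, but does not tie them to the AE tables.

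**The concern.** The proportion of subjects with at least one event, and the number of events, both grow with the time observed. Maximum severity tends to do the same. When the observation windows differ severalfold, a side-by-side table mixes how well a treatment is tolerated with how long it was given.

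Two other features act on the same table. Subjects who never transition stay in the denominators of phases they never entered, which pulls those percentages down. Events that began earlier are added to later phases, which pushes those figures up.

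Tolerability is part of the secondary objective (Protocol 2.2, SAP 2.1.2). A reader of the clinical study report will naturally look across the three columns to see whether prostanoid effects ease or worsen as subjects move to Orenitram. As planned, the table cannot show that.

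**Working it through.** The plan states no AE rate and no per-phase figure, so there is nothing of that kind to reproduce.

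**Phase lengths.** Inputs from SAP 2.2.1 are transition at Day 15, 29 or 57, a transition of 1 to 21 days, and Week 16 at Day 113.

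- Remodulin-only days = transition day − 1
- Orenitram-only days = 113 − (transition day + transition length) + 1

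| Transition visit | Transition days | Remodulin-only | Orenitram-only |
|---|---|---|---|
| Week 2 | 1 | 15 − 1 = 14 | 113 − 16 + 1 = 98 |
| Week 4 | 9 | 29 − 1 = 28 | 113 − 38 + 1 = 76 |
| Week 8 | 1 | 57 − 1 = 56 | 113 − 58 + 1 = 56 |
| Week 8 | 21 | 57 − 1 = 56 | 113 − 78 + 1 = 36 |

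A subject who never transitions has a Remodulin phase of up to about 113 days (16 weeks). With the visit windows, the Orenitram range widens to 24 to 108 days.

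**New onsets at equal risk.** Assume a constant onset rate h per day in every phase, so the proportion with at least one new event is 1 − exp(−h × days). For the Week 4, 9-day case:

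| h (assumed) | Remodulin, 28 d | Transition, 9 d | Orenitram, 76 d |
|---|---|---|---|
| 0.005 | 13.1% | 4.4% | 31.6% |
| 0.01 | 24.4% | 8.6% | 53.2% |
| 0.02 | 42.9% | 16.5% | 78.1% |
| 0.05 | 75.3% | 36.2% | 97.8% |

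At h = 0.01 with 35 subjects, expected new events are 35 × 0.01 × 28 = 9.8, 35 × 0.01 × 9 = 3.15 and 35 × 0.01 × 76 = 26.6. Subject-days are 980, 315 and 2,660. Each ratio is 1.0 per 100 subject-days, which recovers the equal risk.

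**Trade-off within a subject.** Long Remodulin phases go with short Orenitram phases. With a Week 8, 21-day transition and h = 0.01, Remodulin gives 1 − exp(−0.56) = 42.9% and Orenitram 1 − exp(−0.36) = 30.2%. The order is the reverse of the Week 4 case. With a Week 8, 1-day transition both phases last 56 days and the difference vanishes.

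**Carry-over.** Let D be the mean event duration (assumed, 3 to 26 days; 26 is the length of the SAP's example headache). The expected count in a later phase of length T is h × [D × (1 − exp(−prior days / D)) + T].

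- Remodulin against Transition can reverse. With Week 2, a 9-day transition and D = 7, Transition gives 7 × (1 − exp(−14/7)) + 9 = 15.1 per unit h, against 14.0 for the longer Remodulin phase.
- Orenitram against Transition does not. The count ratio ran from 1.4 to 25.4 across transitions at Weeks 2, 4 and 8, lengths of 1, 9 and 21 days, and D = 3, 7, 14 and 26.
- Dividing the SAP's carry-over-inclusive count by phase days would not be a cure. For a 1-day transition at Week 2 it would overstate the onset rate by a factor of 4.0 (D = 3) to 11.8 (D = 26).

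**Denominator.** If a fraction f of the Safety Population never enters a phase, the percentage among those who did is multiplied by (1 − f).

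**Day counting in the optional summary.** The SAP's example reproduces: 10 to 22 January is 12 days and 22 January to 5 February is 14, total 26. The event touches 27 calendar days. SAP 3.3.7 counts exposure as last − first + 1.

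**The case against.** The strongest reply is that the designated secondary safety endpoint for prostanoid effects is not this table but the AE Bothersome Survey (Protocol 10.3.2.1.1, SAP 2.3.2.1). It covers the same seven symptoms with a fixed one-week recall, and its summaries are not optional. A fixed window does not grow with phase length. That stands and limits the damage. But the survey is scheduled only at Baseline, the Transition Visit and Week 16, and the transition value is the last one before Orenitram starts (SAP 3.1.3). No scheduled survey falls within the cross-taper.

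It is also fair that the SAP plans no test and only reports the phases separately, and that SAP 3.3.7 lets a reader see roughly how long each phase lasted. That does not yield an onset rate, because the tabulated event counts mix new and carried-over events.

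Rates are no full cure either. They assume roughly constant risk within a phase, whereas Protocol 1.3 reports anecdotally that AEs leading to discontinuation come early. Dose differs between phases too. New-onset rates alone would miss persistent symptoms, so carried-over events must be shown as well.

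A reader might infer three stronger points, none of which the documents support:

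- *That these tables are the direct evidence for the hypothesis.* Protocol 1.4 sets the hypothesis against patients who start Orenitram de novo, which is a comparison with patients outside this study.
- *That longer phases always look worse.* The trade-off and the carry-over rule show otherwise for Remodulin.
- *That the SAP scores a one-day event as zero days.* It gives one illustration with adjoining severity segments, in an optional summary, and leaves detailed programming to a separate document. The visible discrepancy is one day in 27.

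**Conclusion.** The concern holds in limited form. The by-phase prostanoid AE tables are crude, the nominal phase lengths run from 1 day to 98 days among subjects who transition, and the later-phase denominators include subjects who never got there. At an equal daily onset risk of 0.01, the Week 4, 9-day case shows about 24%, 9% and 53%.

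The direction is secure only for Orenitram against Transition, in subjects who follow the schedule to Week 16. For Remodulin against either of the others, it depends on when subjects transition and how long events last.

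The onset rate, its constancy and the event durations are assumptions. The phase lengths come from the schedule. The consequence is a misleading descriptive table on a secondary objective, with no effect on the primary endpoint. The fix is worth making because it is cheap.

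**What to change.** Keep the crude table in SAP 3.7.1. For each phase and each prostanoid AE, add:

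- the number of subjects who entered the phase, used as the percentage denominator;
- total subject-days in the phase;
- new-onset events per 100 subject-days;
- events carried over from an earlier phase, in a separate row.

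If the optional AE-days summary is produced, divide AE-days by phase-days. State the day-counting rule and make it inclusive, as for exposure in SAP 3.3.7, adding the extra day once, on the final severity segment.

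The cost is a little programming, since the AE dates, reassessment dates and dosing dates are already needed for planned outputs. The rates will be imprecise. In the Week 4, 9-day illustration with all 35 subjects entering, the expected 9.8, 3.15 and 26.6 events imply relative standard errors of about 1/√9.8 = 32%, 1/√3.15 = 56% and 1/√26.6 = 19% under a Poisson assumption. They should be read as descriptive.

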Appendix C. Guidelines and Definitions for Recording Adverse Events

The Investigator or a designated member of his/her staff will probe every subject for any adverse events that could have occurred. The Investigator should always ask the same question when conducting the verbal probe to ensure uniformity between subjects. The Investigator should ask:

"How are you doing (feeling)?"

Based on the subject's response to this question, the Investigator should ask additional questions relevant to the specific complaint such as:

"How severe is/was the symptom?"

"How often did the symptom occur?"

"How long did the symptom last?"

It is the Investigator's responsibility to review the results of all diagnostic and laboratory tests as they become available and ascertain if there is a clinically significant change from Baseline. If the results are determined to be a clinically significant change from Baseline, it should be reported as an adverse event. The Investigator can repeat the diagnostic process or laboratory test or request additional tests to verify the results of the original tests. When possible, a diagnosis associated with the subject's abnormality should be used as the reported adverse event.

Using provided definitions, the Investigator will then:

- 1. Rate the intensity and seriousness of the adverse event
- 2. Estimate the causality of the adverse event to study drug
- 3. Note actions taken to counteract the adverse event

Definitions of Intensity, Seriousness, Causality, Action Taken, and Outcome

Intensity

An assessment of the relative intensity (severity) of an adverse event is based on the Investigator's clinical judgement. The maximum intensity encountered during the evaluation

period should be checked. The assessment of intensity should be independent of the assessment of the seriousness of the adverse event.

Seriousness

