2.3.2 Secondary Endpoints

2.3.2.1 Safety Endpoints

Safety will be assessed using the Prostanoid Adverse Event (AE) scores captured by the AE Bothersome Survey at Baseline, the Transition Visit, and Week 16/Early Study Withdrawal.

The Investigator will administer the AE Bothersome Survey (provided in protocol Appendix E) at time points listed in Table 1 to collect information about prostanoid-related effects experienced by the subject, including headache, diarrhea, nausea, flushing, jaw pain, extremity pain and vomiting. For each prostanoid-related effect, whether the patient has experienced the effect, the degree of bothersome (from 1 - bothers me a lot to 4 - not at all bothersome), and days experiencing it (1 to 7) will be recorded.

Other safety assessments including the incidence of adverse events, clinical laboratory tests, vital signs, and physical examinations are described in Section 3.7.

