3.3.7 Study Drug Exposure

A listing of Orenitram and Remodulin dose levels for each subject at each timepoint will be provided by visit.

A summary of Orenitram and Remodulin dose levels at each study visit will be provided for the Safety Population. Summary of dose levels at each study visit will also be provided for patients who transition at week 2, week 4, and week 8 separately. Change from baseline Remodulin dose levels will also be provided.

Days of exposure to study drug (Remodulin and Orenitram) will be calculated as date of last dose of study drug – date of first dose of study drug + 1. Note that the exposure calculation is intended to describe the length of time a subject was exposed to study drug and therefore does not take study drug interruptions into account. Days of exposure to study drug will be

summarized based on the Safety Population with descriptive statistics and with counts and percentages of subjects with exposure in the following categories:

- <4 weeks (<28 days)
- 4 -<8 weeks (28 55 days)
- 8 <12 weeks (56 83 days)
- 12 <16 weeks (84 111 days)
- ≥16 weeks (≥112 days).

Days of exposure to Remodulin and Days of exposure to Orenitram will also be summarized in the same way.

Number and percentage of subjects who initiated Remodulin in an inpatient vs. outpatient setting will be summarized.

Number and percentage of subjects who initiated Remodulin via IV or SC routes will be summarized

Number and percentage of subjects who switched between IV and SC routes for Remodulin will be summarized

For patients initiating Remodulin in the inpatient setting, the Remodulin dose at discharge will be summarized.

Number and percentage of subjects who initiated transition from Remodulin to Orenitram in an inpatient vs. outpatient setting will be summarized.

Summary statistics will be provided for:

- Time to Transition to Orenitram, calculated as date of first dose of Orenitram date of first dose of Remodulin + 1
- Duration of inpatient stay (for applicable subjects) for Remodulin initiation
- Duration of transition (days receiving both Remodulin and Orenitram)
- Duration of inpatient stay (for applicable subjects) for transition to Orenitram
- Dose of Remodulin (ng/kg/min) at Transition Visit
- Prescribed total daily dose of Orenitram (mg) at the Post-Transition visit

All the above summaries will be based on the Safety Population.

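### The SAP's worked example for days at each AE severity leaves out the AE end date, so each AE with an end date loses one day and a same-day AE would count as zero

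*SAP*

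**What the plan says.** For the seven prostanoid AEs, SAP 3.7.1 says that the days reported, with the matching severity, may be summarized for each treatment phase, and that the sponsor may do this. The dating rule is that "the AE Reassessment date will be used as the start and end dates for an AE which changes in severity". The AE end date closes the AE.

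The section then works through one headache in the Remodulin phase:

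- "AE Start Date: 1/10/2022 severity: mild"
- "AE Reassessment Date 1: 1/22/2022 severity: moderate"
- "AE Reassessment Date 2: 2/01/2022 severity: moderate"
- AE end date 5 February 2022

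The stated result is 12 mild days (10 to 22 January), "Moderate: 14 days (1/22/2022 to 2/5/2022") and 0 severe days. No rule is given for an AE that starts and ends on the same date.

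Two other parts of the SAP count days inclusively:

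- **SAP 3.3.7** takes exposure as the last dose date minus "date of first dose of study drug + 1". It uses the same + 1 for time to transition.
- **SAP 2.3.2.1** says of the AE Bothersome Survey, which covers the same seven symptoms, that "days experiencing it (1 to 7) will be recorded". The scoring table in SAP 3.7.1.1 also starts at 1 day.

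**The concern.** The quantity is described as a number of days on which the AE was reported. The end date is such a day, yet the example assigns it to no severity. The example is the only day-count instruction for this summary, so a programmer would probably copy it.

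The proportional loss is greatest for short events. The documents give no durations for prostanoid AEs, but headache, flushing or vomiting could plausibly begin and end on one date. Such an AE would appear as an event in one table and as 0 days in another. For comparison, a one-day symptom at the worst bother grade scores 8 points in the SAP 3.7.1.1 table. The error always shortens the reported time with an AE.

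**Working it through.** **Inputs** (all from the SAP 3.7.1 example): start 10 January 2022, mild; reassessment 22 January, moderate; reassessment 1 February, moderate; end 5 February.

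**1. Reproduce the SAP's figures** as end date minus start date.

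- Mild: 22 − 10 = 12.
- Moderate: (31 − 22) + 5 = 9 + 5 = 14.
- Total: 12 + 14 = 26.

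Both stated figures match exactly. The second reassessment changes nothing: 22 January to 1 February is 10, 1 to 5 February is 4, and 10 + 4 = 14.

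**2. Count the calendar dates.** 10 to 31 January is 22 dates and 1 to 5 February is 5. The AE is present on 22 + 5 = 27 dates.

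**3. Find the missing date.** Twelve mild days cover 10 to 21 January. Fourteen moderate days cover 22 January to 4 February (10 + 4). The date left over is 5 February, the AE end date. The reassessment date, 22 January, is counted once, under the new severity.

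**4. Try the alternatives.**

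| Rule | Mild | Moderate | Total |
|---|---|---|---|
| End minus start (SAP example) | 12 | 14 | 26 |
| + 1 on both segments | 13 | 15 | 28 |
| + 1 on the last segment only | 12 | 15 | 27 |

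Adding 1 to both segments counts 22 January twice. Adding 1 to the last segment only agrees with the calendar.

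**5. Generalise.** When each segment is end minus start, the segments sum to AE end minus AE start, however many reassessments there are. An AE present on L dates is therefore credited with L − 1 days, a loss of 1/L.

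| Dates present (L) | Days counted | Loss |
|---|---|---|
| 1 | 0 | 100% |
| 2 | 1 | 50% |
| 3 | 2 | 33.3% |
| 7 | 6 | 14.3% |
| 14 | 13 | 7.1% |
| 27 (example) | 26 | 3.7% |

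The lost day always belongs to the severity in force when the AE ended.

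**6. Compare with exposure.** Under SAP 3.3.7, a subject whose first and last doses fall on one date has 0 + 1 = 1 day of exposure. An AE that starts and ends on one date has 0 days under the example's rule.

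**The case against.** **Elapsed time is a legitimate measure.** Protocol 9.2 has sites record onset and cessation dates and times, and 12 and 14 are correct elapsed days. Exposure days and symptomatic days in a week are different quantities, so no sentence is flatly contradicted. The zero for a same-day AE is inferred from one example. It stands that the subtraction is correct and that the zero follows only by applying the example's convention, since no separate rule is stated. The elapsed-time reading does not fit, because the summary is described as days on which the AE was reported and the example uses dates without times.

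**The summary is optional.** This stands and limits the importance. A reader might infer that one-day AEs disappear from the safety report. They do not: SAP 3.7.1 commits to patient counts, event counts and maximum severity by treatment phase, and to by-subject listings. Nor does either document make this summary the test of whether tolerability improves.

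**A stronger reading is tempting.** Protocol Appendix C asks for "The maximum intensity encountered during the evaluation" period, and the 1 February reassessment shows no change in severity. A reader might infer that grades look back, that the SAP wrongly applies them forward, and that severity lands in the wrong phase. The documents do not establish this:

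- The evaluation period is undefined, and Appendix C does not mention reassessment records.
- The documents do not say whether the reassessment date is the date the severity changed. The unchanged reassessment creates no split, so it says nothing about 22 January.
- Protocol 3.3.2.5 requires contact at least weekly, and daily in the first 2 weeks and during transition. Long gaps in dating cannot be assumed.
- Back-dating each grade would turn the example's 12 mild days into 0 and leave the days after 1 February without a rule.

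**Conclusion.** The point holds as a small, definite inconsistency in an optional descriptive summary. The example credits 26 days to an AE present on 27 dates. Applied generally, its rule removes one day from each AE with an end date and gives a same-day AE no days at all. The relative loss runs from 3.7% in the example to 100% for a one-day AE.

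This rests on three assumptions: the summary is meant to count days with the AE present, the example's convention is applied to all AEs, and the sponsor produces the summary. The effect on the summary as a whole depends on the mix of AE durations, which the documents do not give. The committed AE tables, the listings and the efficacy endpoints are not affected. The finding does not extend to how severity grades are dated.

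**What to change.** In SAP 3.7.1:

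- Keep the split at the reassessment date, with that day counted once, under the new severity.
- Count the segment that ends on the AE end date as AE end date minus segment start date + 1. The + 1 is added once per AE, not at each split.
- State that an AE starting and ending on the same date counts as 1 day, at its recorded severity.
- Correct the example to Mild 12, Moderate 15, Severe 0, total 27.

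The cost is a few lines of SAP text and the matching program change. No new data are needed. Day counts rise by one for each AE with an end date.
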